### 4.1.3. Per-Protocol Analysis Set: Infant Participants (Stages 2 and 3)

The evaluable immunogenicity population will include participants:

 Who are eligible (mother has signed informed consent and met all inclusion/exclusion criteria) and whose mother was randomized into the study. If the mother is not eligible for the study, her infant(s) will not be eligible for the study as well.

- Whose mother has received GBS6 or placebo as randomized;
- Who have cord blood available, or blood drawn for assay testing within 72 hours after birth (Visit 1);
- Who have at least 1 valid and determinate assay result at the birth visit (Visit 1);
- Who have no major protocol violation as determined by the sponsor's global medical monitor.

### 4.1.4. Per-Protocol Analysis Set: Maternal and Infant Pairs (Stages 2 and 3)

This evaluable immunogenicity population will include the maternal and infant pairs who are in their respective evaluable immunogenicity populations.

#### 4.2. Full Analysis Set

In this study, the full analysis set will be referred to as the mITT population.

The immunogenicity data based on the mITT population for nonpregnant women (Stage 1), and maternal participants (Stages 2 and 3) will be summarized according to the vaccine group as randomized. The immunogenicity data for infant participants (Stages 2 and 3) will be summarized according to the vaccine group as randomized to their mothers.

The immunogenicity results based on the mITT population will be summarized for secondary immunogenicity endpoint(s) within each stage of the study only if there is a sizable difference (eg,  $\sim$ 10%) in the number of participants between the mITT and evaluable immunogenicity populations.

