10.2.1. Immunogenicity Analysis Populations

For the immunogenicity analyses, 2 analysis populations will be defined separately for nonpregnant women, maternal participants, and their infant participants: evaluable immunogenicity and modified intent to treat (mITT) populations.

For the immunogenicity analyses, nonpregnant and maternal participants will be analyzed according to the investigational product received for the evaluable immunogenicity population and the investigational product as randomized for the mITT population. Infant participants will be analyzed according to the investigational product received by their mothers (maternal participants) for the evaluable immunogenicity population and the investigational product assigned to their mothers (maternal participants) for the mITT population. The evaluable immunogenicity population is considered to be the primary population for the immunogenicity analyses.

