#### 4.1. Per-Protocol Analysis Set

In this study, the per-protocol analysis set will be referred to as the evaluable immunogenicity population. The evaluable immunogenicity population will be the primary population for all immunogenicity data analyses.

The immunogenicity data based on the evaluable immunogenicity population for nonpregnant women (Stage 1), and maternal participants (Stages 2 and 3) will be summarized according to the vaccine group as administered, which by the population definition is equivalent to the vaccine group as randomized. The immunogenicity data for infant participants (Stages 2 and 3) will be summarized according to the vaccine group as administered to their mothers.

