#### 4.5. Vaccine Misallocations

• Randomized but not vaccinated: this group includes nonpregnant women (Stage 1) and maternal participants (Stages 2 and 3) who were randomized but not vaccinated and infant participants (Stages 2 and 3) whose mothers were randomized but not vaccinated. These participants will not be included in the safety population for safety analyses. These participants will not be included in the evaluable immunogenicity population, but they will be included in the mITT population for immunogenicity analyses for participants with valid and determinant assay results. The immunogenicity results for these participants will be reported under the vaccine group as randomized or as their mothers were randomized in the case of infant participants.

- Vaccinated but not randomized: this group includes nonpregnant women (Stage 1) and
  maternal participants (Stages 2 and 3) who were vaccinated but not randomized and
  infant participants (Stages 2 and 3) whose mothers were vaccinated but not randomized.
  These participants will be included in the safety population for safety analyses and will
  be reported under the vaccine group based on the vaccine they received, or the vaccine
  received by their mothers in the case of infant participants. They will be excluded from
  immunogenicity analyses based on either the evaluable immunogenicity or mITT
  population.
- Randomized but received incorrect vaccine: this group includes nonpregnant women (Stage 1) and maternal participants (Stages 2 and 3) who were randomized but received an incorrect vaccine and infant participants (Stages 2 and 3) whose mothers were randomized but received an incorrect vaccine. These participants will be included in the mITT population for immunogenicity analyses if any assay results are available and will be reported under the vaccine group based on their or their maternal (for infants) randomized vaccine group in the analysis. These participants will also be included in the safety population for safety analysis and will be reported under the vaccine group based on the vaccine they or their mothers (for infants) received. These participants will be excluded from the evaluable immunogenicity population for immunogenicity analyses.

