#### 6.2.2. Secondary Endpoint(s): Maternal Participants (Stages 2 and 3)

# 6.2.2.1. GBS6 Serotype-Specific IgG GMCs Measured at 2 Weeks and 1 Month After Vaccination and at Delivery in Maternal Participants

Endpoints: GBS6 serotype-specific IgG antibody concentrations.

- Analysis time points: 2 Weeks and 1 month after vaccination and at delivery.
- Analysis population: Evaluable immunogenicity and mITT (provided there is a sizable difference with evaluable) populations for maternal participants (Stages 2 and 3).
- Analysis methodology: Descriptive summary statistics and MMRM.
- Supporting objective: Secondary objective.

- Raw data: The number of participants with valid assay data (n), GMCs, and associated 2-sided 95% CI will be presented for each analysis time point and serotype, by vaccine group.
- GMCs and associated 95% CI from the MMRM analysis specified in Section 6.3.3.1.

Figures: The following figures will be based on the evaluable immunogenicity population only.

 Empirical RCDCs for the time points at 1 month after vaccination and at delivery will be generated separately for each serotype, by vaccine group.

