## 9. APPENDICES

Table 11. Summary of Immunogenicity and Colonization Data Analyses (Excluding Subgroup)

Stage(s)	Population	Sample	Outcome	Analysis	Analysis Time Points	Data Type
1 (Nonpregnant women)	Evaluable immunogenicity population for nonpregnant women	Blood	GBS6 serotype-specific IgG, primary vaccination	GMCs and CCI from the primary vaccination Day 1 to each postvaccination time point, along with respective 95% CIs	Day 1 (before the primary vaccination) and 2 weeks and 1 month after the primary vaccination	Continuous
				Proportion of participants achieving a defined IgG level (eg, 1.0 μg/mL) and corresponding 95% CIs	Day 1 (before vaccination) and 2 weeks and 1 month after the primary vaccination	Binary
				RCDCs	1 Month after the primary vaccination	Continuous
				Antibody response curves	Day 1 (before the primary vaccination) and 2 weeks and 1 month after the primary vaccination	Continuous
				GMCs at each analysis time point based on the mITT population, if the proportion of participants in the mITT population differs from that of the evaluable immunogenicity population by at least 10%	Day 1 (before the primary vaccination) and 2 weeks and 1 month after the primary vaccination	Continuous
			GBS6 serotype-specific IgG, booster vaccination	GMCs and COL of the booster vaccination from before to each postvaccination time point, along with respective 95% CIs	Prebooster Day 1 (before the booster vaccination) and 1 month, 3 months, and 6 months after the booster vaccination	Continuous

Table 11. Summary of Immunogenicity and Colonization Data Analyses (Excluding Subgroup)

Stage(s)	Population	Sample	Outcome	Analysis	Analysis Time Points	Data Type
				Proportion of participants achieving a defined IgG level (eg, 1.0 μg/mL) and corresponding 95% CIs	Prebooster Day 1 (before the booster vaccination) and 1 month, 3 months, and 6 months after the booster vaccination	Binary
				RCDCs	Prebooster Day 1 (before the booster vaccination) and 1 month, 3 months, and 6 months after the booster vaccination	Continuous
				Antibody response curves	Prebooster Day 1 (before the booster vaccination) and 1 month, 3 months, and 6 months after the booster vaccination	Continuous

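### The as-randomised (mITT) immunogenicity results depend on a stage-wide size trigger of about 10%, so a loss concentrated in one vaccine group can leave them unreported

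*SAP*

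**What the plan says.** SAP 4.1 fixes the main population: "The evaluable immunogenicity population will be the primary population for all immunogenicity data analyses". SAP 4.2 then says that the mITT results "will be summarized for secondary immunogenicity endpoint(s) within each stage of the study only if there is a sizable difference" and describes that difference as one "in the number of participants between the mITT and evaluable immunogenicity populations", with about 10% given as an example.

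The 6.2 subsections carry the condition for every secondary immunogenicity endpoint. SAP 6.2.2.1, for instance, lists as the second population "mITT (provided there is a sizable difference with evaluable) populations for maternal participants (Stages 2 and 3". SAP Table 11, in the Stage 1 primary-vaccination rows, words it more firmly: mITT GMCs are given "if the proportion of participants in the mITT population differs from that of the evaluable immunogenicity population by at least 10" per cent. None of these places ties the comparison to a vaccine group.

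Protocol 10.2.1 defines "evaluable immunogenicity and modified intent to treat (mITT) populations", names the evaluable set as primary and attaches no reporting condition. On women given the wrong product, and their infants, SAP 4.5 says "These participants will be excluded from the evaluable immunogenicity population for immunogenicity analyses"; it keeps them in the mITT set under their randomised group. SAP 6.6.2.2 provides unconditional summaries and listings of exclusions with reasons, a tabulation by group of draws inside and outside the time frame, and a listing of participants not vaccinated as randomised.

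**The concern.** Apart from the single-group booster analysis, each secondary immunogenicity result is a GMC or GMT for one vaccine group (for infants, one maternal vaccine group). Selection after randomisation distorts such an estimate according to the loss in that group, not the average loss over the stage. The trigger measures only the average. It is least informative in Stage 2, where seven groups share one count and each GBS6 group is one ninth of the women.

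At stake is a supportive check. If losses were concentrated, a reader of the study report could have only estimates from a population selected after randomisation, with no as-randomised estimate beside them. The Stage 2 data were planned as the basis for choosing the dose and formulation, and the Stage 3 data are meant to support development decisions and regulatory discussions (SAP 7.2).

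**Working it through.** **Step 1. Who can make the two sets differ.** The mITT set needs randomisation and at least one valid assay result (SAP 4.2.2). The maternal evaluable set (SAP 4.1.2) also needs eligibility, the correct product, a Visit 3 draw on Days 27 to 49 (or, if there is no 1-month visit, a delivery draw within 72 hours and before Day 49), and no major violation. An excluded participant matters only where she still has a result:

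- a recipient of the wrong product, or a woman with a major violation: any time point with a result;
- a woman whose Visit 3 draw fell outside the window: that draw and her other samples;
- a woman with no Visit 3 sample who delivers after Day 49: only her 2-week and delivery values. She has no 1-month value in either set, since SAP 5.3.1 does not impute.

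Infant evaluability (SAP 4.1.3) does not depend on the mother's Visit 3 draw. Birth values can differ between the sets only through maternal ineligibility, wrong product, draws after 72 hours or major violations.

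**Step 2. Inputs.** Stage 2: six GBS6 groups of 40 plus 120 placebo (Protocol 10.1). Check: 6 × 40 + 120 = 360, the plan's own total. Stage 3: 108 + 108 = 216 (Protocol 10.1), or 98 + 98 = 196 in the SAP, which is based on Protocol Amendment 7. Stage 1: 3 × 22 = 66. Assumption: the mITT set equals the planned number. Maternal and infant sets are counted separately; the figures below are for the women.

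**Step 3. Largest loss below 10% of the stage, all in one group (worst case).**

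| Stage | Most exclusions below 10% | Share of one group |
|---|---|---|
| 1 | 6/66 = 9.1% | 6/22 = 27% |
| 2, GBS6 group | 35/360 = 9.7% | 35/40 = 87.5% |
| 2, placebo | 35/360 = 9.7% | 35/120 = 29% |
| 3, protocol size | 21/216 = 9.7% | 21/108 = 19.4% |
| 3, SAP size | 19/196 = 9.7% | 19/98 = 19.4% |

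A less extreme Stage 2 case: 20 of 40 in one group is 20/360 = 5.6%.

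**Step 4. Sensitivity.** SAP 4.2 does not name the denominator. With the evaluable size as denominator, the Stage 2 limit is 32 (32/328 = 9.8%), or 32/40 = 80% of one group; the Stage 3 limit is 19 (19/197 = 9.6%), or 19/108 = 17.6% of one arm. If the other groups lose an assumed 5%, Stage 2 leaves 35 − 16 = 19 for one group (19/40 = 47.5%), and Stage 3 leaves 21 − 5 = 16 (16/108 = 14.8%).

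**Step 5. Possible effect on a GMC.** If a fraction f of a group is excluded, all have a result at the time point, and their IgG is k-fold lower than that of the others, then evaluable GMC / mITT GMC = k^f. With f = 0.194: 2^0.194 = 1.14 and 4^0.194 = 1.31. Both f and k are assumptions; the documents give neither.

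**The case against.** The case on the other side is substantial.

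- **The loss is not hidden.** SAP 6.6.2.2 reports exclusions, draw timing and misallocations whatever the trigger says. This stands. A reader might infer that a concentrated loss would go unseen, and the documents do not support that. What stays unseen is the effect on the estimates.
- **The 10% is only an example in SAP 4.2.** True, so the sponsor may show mITT results below it. But nothing requires this, and the visible Table 11 wording is firmer.
- **The protocol is not breached.** A reader might infer a conflict with Protocol 10.2.1. That section defines both populations but does not promise that both will always be tabulated, and Protocol 10 lets the SAP modify the protocol's outline.
- **One-group loss is a constructed extreme.** Populations are classified before unblinding (SAP 4), and participants, assessors and assay staff are blinded (Protocol 6.7 and 6.8). The counts in Step 3 are therefore limits of the rule, not expected losses.
- **mITT is not a clean comparator.** It too depends on having a valid result after randomisation, and participants without one are in neither set and do not count toward the 10%. It is still the wider set, and the only one that keeps the randomised grouping for recipients of the wrong product.
- **Immunogenicity is secondary and descriptive.** No hypothesis is tested (SAP 5.1), so no error rate is affected, and the primary safety endpoints are untouched. This limits the weight of the point. It also means that the group estimates and their intervals are what readers will use.

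**Conclusion.** The point holds as a weakness in a reporting rule. The trigger is set on total population size within a stage, while the results are read by group. It can therefore stay silent with half of one Stage 2 GBS6 group excluded (5.6% of the stage) or 19.4% of one Stage 3 arm excluded (9.7% of the stage). The Stage 3 share is the same with the protocol's 216 or the SAP's 196. These are worst-case placements that assume the mITT set equals the planned number.

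The documents do not show that such a loss will occur or that any GMC or GMT is biased. A reader might take the 1.14- to 1.31-fold figure as an expected bias; it is only an illustration under the assumptions in Step 5. Nor does every missed Visit 3 draw, or any infant's birth value by way of the mother's Visit 3 draw, come into play. The change is a cheap improvement and does not correct an error in a main analysis.

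**What to change.** In SAP 4.2, in the 6.2 subsections and in Table 11, delete the size condition. State that the mITT GMCs and GMTs for the secondary immunogenicity endpoints will always be reported with 95% CIs, by randomised group (for infants, the mother's randomised group), beside the evaluable results. Keep the evaluable set as primary; the figures can stay on the evaluable set alone. This also removes the difference in wording between SAP 4.2 (an example, on numbers) and Table 11 (a fixed minimum, on proportions).

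A 10% trigger within each group is not a good substitute. Four exclusions in a group of 40 would set it off. With an assumed uniform 5% loss, the chance is 0.138 for each GBS6 group and 0.017 for placebo (12 of 120), so at least one Stage 2 group would trip it with probability 1 − (1 − 0.138)^6 × (1 − 0.017) ≈ 0.60.

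The cost is SAP wording and a few more supportive tables from data already held.

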### 4.2.1. Full Analysis Set: Nonpregnant Women (Stage 1)

The primary vaccination mITT population will include all randomized participants who have at least 1 valid and determinate assay result.

The booster vaccination mITT population will include all randomized participants who received a booster dose and have at least 1 valid and determinate assay result.

### 4.2.2. Full Analysis Set: Maternal Participants (Stages 2 and 3)

All randomized participants who have at least 1 valid and determinate assay result will be included in the mITT population.

#### 4.2.3. Full Analysis Set: Infant Participants (Stages 2 and 3)

All infants of randomized maternal participants who have at least 1 valid and determinate assay result will be included in the mITT population.

#### 4.3. Safety Analysis Set

In this study, the safety analysis set will be referred to as the safety population. A safety population will be defined separately for nonpregnant women and maternal participants and their infant participants. The safety population is the analysis population for all the safety endpoints.

The safety data for nonpregnant women with primary and booster vaccinations (Stage 1) and maternal participants (Stage 2 and 3) will be summarized according to the vaccine group as administered. The safety data for infant participants (Stages 2 and 3) will be summarized according to the vaccine group as administered to their mothers.

# 4.3.1. Safety Analysis Set: Nonpregnant Women (Stage 1)

All participants who received a primary dose of GBS6 vaccine or placebo will be included in the primary vaccination safety population.

All participants who received a booster dose of GBS6 will be included in the booster vaccination safety population.

#### 4.3.2. Safety Analysis Set: Maternal Participants (Stages 2 and 3)

All participants who received the GBS6 vaccine or placebo will be included in the safety population.

# 4.3.3. Safety Analysis Set: Infant Participants (Stages 2 and 3)

All infants whose mother received the GBS6 vaccine or placebo will be included in the safety population.

#### 4.4. Other Analysis Sets

No other analysis sets will be defined in this study.

#### 4.5. Vaccine Misallocations

• Randomized but not vaccinated: this group includes nonpregnant women (Stage 1) and maternal participants (Stages 2 and 3) who were randomized but not vaccinated and infant participants (Stages 2 and 3) whose mothers were randomized but not vaccinated. These participants will not be included in the safety population for safety analyses. These participants will not be included in the evaluable immunogenicity population, but they will be included in the mITT population for immunogenicity analyses for participants with valid and determinant assay results. The immunogenicity results for these participants will be reported under the vaccine group as randomized or as their mothers were randomized in the case of infant participants.

- Vaccinated but not randomized: this group includes nonpregnant women (Stage 1) and
  maternal participants (Stages 2 and 3) who were vaccinated but not randomized and
  infant participants (Stages 2 and 3) whose mothers were vaccinated but not randomized.
  These participants will be included in the safety population for safety analyses and will
  be reported under the vaccine group based on the vaccine they received, or the vaccine
  received by their mothers in the case of infant participants. They will be excluded from
  immunogenicity analyses based on either the evaluable immunogenicity or mITT
  population.
- Randomized but received incorrect vaccine: this group includes nonpregnant women (Stage 1) and maternal participants (Stages 2 and 3) who were randomized but received an incorrect vaccine and infant participants (Stages 2 and 3) whose mothers were randomized but received an incorrect vaccine. These participants will be included in the mITT population for immunogenicity analyses if any assay results are available and will be reported under the vaccine group based on their or their maternal (for infants) randomized vaccine group in the analysis. These participants will also be included in the safety population for safety analysis and will be reported under the vaccine group based on the vaccine they or their mothers (for infants) received. These participants will be excluded from the evaluable immunogenicity population for immunogenicity analyses.

#### 5. GENERAL METHODOLOGY AND CONVENTIONS

### 5.1. Hypotheses and Decision Rules

# 5.1.1. Statistical Hypotheses

This is a Phase 1/2 randomized, placebo-controlled, observer-blinded study to assess safety, tolerability, and immunogenicity of GBS6 in healthy nonpregnant as well as pregnant women and their infant participants. In all 3 stages of the study, no formal statistical hypothesis testing will be performed. An estimation approach will be used to assess the safety and immunogenicity objectives.

#### 5.1.2. Statistical Decision Rules

Statistical decision rules will not be utilized in this study. All analyses are considered descriptive in nature.

#### 5.2. General Methods

Descriptive summary statistics will be provided for all endpoints. Unless otherwise explicitly stated, the descriptive statistics for continuous variables are: n, mean, median, standard deviation, minimum, and maximum. The descriptive statistics for categorical variables are: the proportion (%), n (the numerator), and N (the denominator) used in the proportion calculation.

The dose/formulation level and vaccine group (hereafter referred to as vaccine group) in this study are defined as below:

- GBS6 (5 μg)/AlPO4
- GBS6 (5 μg)/no AlPO4
- GBS6 (10 μg)/AlPO4
- GBS6 (10 μg)/no AlPO4
- GBS6 (20 μg)/AlPO4
- GBS6 (20 μg)/no AlPO4
- Placebo

All safety and immunogenicity summaries in each stage of the study will be presented by a subset or complete set dependent on the study stage. In Stage 1 for primary vaccination, the subset will only include Groups 5 through 7; Stage 1 for booster vaccination will only include GBS6 (20  $\mu$ g)/AlPO4; Stage 2 will include all vaccine groups; Stage 3 will only include GBS6 (20  $\mu$ g)/no AlPO4 and placebo. Unless otherwise explicitly stated, all Stage 2 maternal participants from both sentinel and expanded cohorts will be combined, by vaccine groups listed above. Similarly, all Stage 2 infant participants from both sentinel and expanded cohorts will be combined according to their mother's vaccine group.

Both safety and immunogenicity results will be summarized separately for nonpregnant women with primary vaccination (Stage 1), nonpregnant women with a booster vaccination (Stage 1), maternal participants in Stage 2, maternal participants in Stage 3, infant participants in Stage 2, and infant participants in Stage 3. Immunogenicity data from Stage 3 will also be summarized separately by country (USA/UK, South Africa).

The GBS6 IgG antibody levels will be standardized as current quantitated values × correction factor. The lower limit of quantitation (LLOQ) values will be standardized as LLOQ = LLOQ × correction factor. The correction factors are set as follows: Ia, 0.46628125; Ib, 0.463392157; II, 1.451696809; III, 0.727236264; IV, 0.686258373; and V, 0.236850746. The standardized quantitated values will be reported for all analyses.

